## 2. Population of analysis

We will conduct an intention to treat (ITT) analysis as well as a per protocol (PP) analysis. ITT will serve as our primary analysis. For PP analyses, individuals in the intervention group will be considered members of the control group if they did not receive or did not interact with the DST for even one minute.

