- Research staff will give the tablet-based DST to participants randomized to the intervention arm to complete prior to their visit.
- All participants will then have a clinical visit with their healthcare provider, per standard clinic protocol.
 - During the visit, participants who are randomized and consented to audio-recordings will have their visits audio-recorded on a HIPAA-compliant recorder.
- After the clinical visit, each study participant will complete a post-visit survey about their demographics, HIV prevention method choice and experience of the counseling they received. If a participant must leave the clinic without completing her post-visit survey due to time constraints (and not because she wants to withdraw from the study), study staff will attempt to contact the participant using the contact information provided and request that they complete the post-visit survey by phone or email.
 - If the patient does not complete the post-visit survey within 72 hours of their initial visit, study personnel will continue to attempt to have them complete the post 72-hours version of the post-survey (in which the time-sensitive questions pertaining to satisfaction with choice and quality of interpersonal care have been omitted) up to one month after the initial visit.
- Participants will receive a \$20 gift certificate after completion of post-visit survey on the day of enrollment. If a participant does not complete the post-survey on the day of their appointment a \$20 gift certificate will be sent by mail after completing the survey by the RA.
- After completing the post-visit survey, participants who completed an audio-recorded session will receive an additional \$20 gift certificate.
- After the post-visit survey, participants who consented to participate in an in-depth interview will complete the interview in a private room in the clinic immediately following their appointment (in person or via video conference), or schedule the interview with research staff to take place within one week of the visit. After completion of the interview, participants will be compensated with a \$40 gift certificate. Details regarding interview procedures can be found in Section 7.4.
- Study staff will provide each patient with a flyer summarizing the timing of follow-up at three months and providing contact information for study staff in case a participant changes their contact information or wishes to dis-enroll.

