### 1.5 Sample size calculation

Using standard methods, we estimate that a sample of 320 women will provide 80% power in two-sided tests with alpha of 0.05 to detect a between-group difference of 10 percentage points in PrEP uptake, from 5% among controls to 15% in the intervention arm. This estimate is conservative, for two reasons. First, in addition to multiple imputation, which will capture some information from women with missing 3-month outcomes, we will enroll 384 women to protect against a loss to follow-up of up to 20%. Second, because women rather than providers will be randomized, any within-provider clustering of outcomes will increase precision in the proposed mixed models including random effects for provider.

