## 2.2 Hypotheses

1. The intervention will result in significantly higher number of PrEP prescriptions compared to the control group.
2. The intervention will result in significantly higher number of individuals reporting PrEP initiation compared to the control group.
3. The intervention will result in significantly higher level of patient-perceived HIV risk post-visit compared to the control group.
4. The intervention group will report significantly higher PrEP knowledge compared to the control group.
5. The intervention group will report significantly higher quality of HIV care compared to the control group.
6. The intervention group will report significantly higher intention to initiate any HIV prevention method compared to the control group.
7. The intervention group will report significantly higher satisfaction with information received about HIV prevention compared to the control group.
8. The intervention group will report significantly higher confidence in decision to use an HIV prevention method compared to the control group.
9. The intervention group will report significantly higher acceptability of HIV prevention methods compared to the control group.
10. The intervention group will report significantly lower decisional conflict, as documented by the full scale and subscales, compared to the control group.
11. The intervention will result in significantly higher number of individuals reporting ongoing PrEP use at 3 months post-visit compared to the control group.
12. A significantly higher proportion of the intervention group will report use of any HIV prevention method at 3 months-post study initiation compared to the control group.
13. A significantly higher proportion of the intervention group will report significantly higher continuation of any HIV prevention method at 3 months-post study initiation compared to the control group.
14. The intervention group will report high acceptability of the DST.
15. A high proportion of the intervention group will report positive impression of the DST.
16. A high proportion of the intervention group will report willingness to use the DST at a future visit.
17. A high proportion of the intervention group will report willingness to recommend to a friend.
18. The intervention group will report high satisfaction with the DST.

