#### 3.3.1 Primary analysis (H1)

PrEP prescriptions within 3 months of primary study visit will be extracted from participants' electronic medical records (EMRs). Data will be matched to survey data using participant medical record numbers (MRNs). Summary statistics will be presented by treatment group. Differences in PrEP prescriptions between groups will be examined by  $\chi^2$  or Fisher's exact-tests as appropriate. Effect size will be calculated.

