#### 3.3.2 Secondary data analyses

The analysis plan for H2-H9 is as follows:

Summary statistics will be presented by treatment group. Differences between study groups at  $t_1$  will be assessed through  $\chi^2$  or Fisher's exact tests as appropriate. Cohen's d will be calculated as measure for effect size.

The analysis plan for H10 is as follows:

Full scale and subscales will be scored as instructed in the [Decisional Conflict Scale](#) manual. Summary statistics will be presented by treatment group for the full scale and by subscale. To assess differences in scale score distribution between groups, we will perform t-tests or sign tests as appropriate. In case of high positive skew (as common in the literature) we will create binary variables demarcating no conflict versus any conflict and perform  $\chi^2$  tests. Cohen's d will be calculated as measure for effect size.

The analysis plan for H11-H13 is as follows:

Summary statistics will be presented by treatment group. Differences between study groups at  $t_2$  will be assessed through  $\chi^2$  or Fisher's exact tests as appropriate. Cohen's d will be calculated as measure for effect size.

The analysis plan for H14-H18 is as follows:

Summary statistics will be presented for the intervention group.

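### The per-protocol analysis counts DST-arm non-users as controls; this is an as-treated comparison that no longer rests on randomisation

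*SAP*

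**What the plan says.** SAP section 2 plans two analyses, ITT and per protocol, and states that "ITT will serve as our primary analysis". For the per-protocol analyses, "individuals in the intervention group will be considered members of the control group if they did not receive" the tool or "did not interact with the DST for even one minute". These women are neither dropped nor kept in their randomised arm; they join the comparison group.

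Use of the tool is settled after randomisation. SAP 1.6 places access to the tablet after the REDCap allocation, and Protocol 3.2.3 says: "Research staff will give the tablet-based DST to participants randomized to the intervention arm to complete prior to their visit". The tool takes about 10 minutes (Protocol 1.1).

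The between-group tests in the SAP are unadjusted. For the primary outcome (SAP 3.3.1), "Differences in PrEP prescriptions between groups will be examined by" chi-square or Fisher's exact test. SAP 3.3.2 uses the same tests for the other between-group hypotheses, except decisional conflict: "To assess differences in scale score distribution between groups, we will perform t-tests or sign tests as appropriate", with a chi-square fallback for strong skew. No hypothesis in SAP 2.2 and no paragraph of SAP 3.3.1–3.3.2 mentions the per-protocol set. H1, for example, reads only: "The intervention will result in significantly higher number of PrEP prescriptions compared to the control group".

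**The concern.** A per-protocol set normally leaves out women who did not follow their allocation. This rule moves them to the other arm, which makes the analysis as-treated. The regrouped DST group is then a self-selected or circumstance-selected part of one arm, and the regrouped control group is the whole control arm plus the remainder of the DST arm. If the women who skip the tool would have taken up PrEP at a different rate anyway, the two groups differ before the tool has any effect. The tests described in the SAP do not correct for that.

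At stake is a supportive result that carries a per-protocol label but could differ from ITT for reasons unrelated to the tool. The primary conclusion is not at stake. The rule is written for per-protocol analyses in general, so it could also be applied to the secondary between-group outcomes.

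**Working it through.** **Inputs from the documents.** 192 women per arm (SAP 1.2); planning rates "from 5% among controls to 15% in the intervention arm" with two-sided alpha 0.05 (SAP 1.5). The planned total of 320 reproduces with the continuity-corrected two-proportion formula (160 per arm; 282 in total without the correction). It does not depend on the per-protocol rule.

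**Assumed, because the documents give no figure.** f, the fraction of the DST arm counted as non-users, and pn, PrEP uptake in those women. Under one minute of use is taken to have no effect.

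**Bias formula.** Let p be control-arm uptake and Δ the true effect in users.
- Users' uptake without the tool: (p − f·pn)/(1 − f)
- Uptake in the regrouped control group: (p + f·pn)/(1 + f)
- Regrouped difference: Δ + (p − f·pn)/(1 − f) − (p + f·pn)/(1 + f) = Δ + 2f(p − pn)/(1 − f²)

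The bias favours the tool if pn < p, is zero if pn = p, and reverses if pn > p. It does not depend on Δ.

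**No tool effect, p = 5%, pn = 1%.** Type I error is by exact binomial enumeration. For chi-square (uncorrected) the two figures take the number of non-users as fixed and as binomial; for Fisher it is fixed.

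| f (non-users) | Bias, points | Chi-square | Fisher |
|---|---|---|---|
| 2% (4) | +0.2 | 4.8%, 5.0% | 3.8% |
| 5% (10) | +0.4 | 5.1%, 5.3% | 4.2% |
| 10% (19) | +0.8 | 6.6%, 6.6% | 5.1% |
| 20% (38) | +1.7 | 11.2%, 12.0% | 9.6% |
| ITT | 0 | 4.9% | 2.8% |

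Example, f = 5%: 2 × 0.05 × (0.05 − 0.01)/(1 − 0.0025) = 0.0040.

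**Sensitivity to pn at f = 5%.** pn = 0%: +0.5 points; 5%: 0; 15%: −1.0.

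**Under the planning effect.** Controls 5%, with 15% taken as uptake in users; all differences in points.

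| f | pn | True effect in users | Regrouped | ITT | ITT/(1 − f) |
|---|---|---|---|---|---|
| 5% | 5% | 10.0 | 10.0 | 9.5 | 10.0 |
| 5% | 15% | 10.5 | 9.5 | 10.0 | 10.5 |
| 5% | 1% | 9.8 | 10.2 | 9.3 | 9.8 |
| 20% | 5% | 10.0 | 10.0 | 8.0 | 10.0 |
| 20% | 15% | 12.5 | 8.3 | 10.0 | 12.5 |
| 20% | 1% | 9.0 | 10.7 | 7.2 | 9.0 |

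The pn = 5% rows have no bias although users exceed non-users; the pn = 15% rows are biased although the two are equal. Comparing observed uptake in users and non-users therefore cannot diagnose the problem, because users' uptake includes any tool effect.

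**Could the trial data show which case holds?** Hardly. With 10 non-users, zero prescriptions has probability 0.99¹⁰ = 90% if pn = 1% and 0.95¹⁰ = 60% if pn = 5%. The exact 95% interval for 0 of 10 is 0–31%.

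**The case against.** The strongest reply is that little depends on this analysis. ITT is primary, and the per-protocol set has no hypothesis or analysis paragraph of its own; that it would use the SAP's unadjusted tests is an inference. At 2–5% non-use with pn = 1%, the bias is 0.2–0.4 points against a planned difference of 10, and chi-square type I error is practically that of ITT. Fisher's test, also allowed by SAP 3.3.1, stays at or below about 5% up to 10% non-use. This stands and limits the severity. Fisher's lower rate reflects its conservatism (2.8% under ITT); the bias in the estimate is the same.

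Second, nothing in the documents supports pn = 1%. Non-receipt may be logistical and unrelated to interest in PrEP, in which case the bias is near zero. That is fair: the size is conditional, and neither its sign nor its presence can be known in advance.

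Third, low non-use is a judgement. It is plausible, since staff hand over the tablet before the visit and one minute counts as use. But Protocol section 5 lets recruitment and baseline activities take place before, during or after the appointment, so some women may not get the tool in time. Higher non-use would enlarge any bias.

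Fourth, the rule is stated openly, so relabelling would cure the clear error, and a complier-average estimate is a preference. That is accepted: the estimate is optional below. Simply excluding non-users would match the label, but it still breaks randomisation. Its bias is f(p − pn)/(1 − f), about half that of the regrouping at 5% non-use: 0.05 × 4/0.95 = 0.2 points against 0.4.

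**Conclusion.** The concern holds. As written, the rule produces an as-treated comparison under a per-protocol label, and it is biased unless would-be users and non-users have the same PrEP uptake without the tool. The label is wrong whatever the amount of non-use; the size of the bias depends on f and pn, both assumed. At the low non-use that seems most likely (2–5%), the bias is a few tenths of a point at pn = 1%, and between +0.5 and −1.0 points at 5% non-use for pn from 0% to 15%. It becomes material only with substantial non-use: at 20%, +1.7 points with pn = 1% and no tool effect, or 8.3 reported against a true 12.5 with pn = 15% under the planning effect. The primary ITT result and the sample size are unaffected. The change should be made, but the validity of the main conclusion does not depend on it.

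**What to change.** - In SAP section 2, delete the reassignment rule and keep every woman in her randomised arm.
- Report the proportion of the DST arm counted as non-users, split into not received and received but used for under one minute, and state how use time is recorded.
- If an effect in users is wanted, add for the primary outcome only, as supportive, a complier-average estimate: the ITT risk difference divided by the proportion of the DST arm using the tool, with a 95% CI. Controls have no access to the tool (SAP section 1). State the exclusion restriction, that assignment does not change prescribing in women counted as non-users, and note that brief use may violate it.
- At minimum, if the regrouping stays, call it as-treated and exploratory and say that it is not a randomised comparison.

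**Cost.** SAP wording and, if wanted, one short analysis. At p = 5% and pn = 1% with no tool effect, the complier-average standard error is 2.34 points against 2.23 for the regrouping at 5% non-use (about 5% wider), and 2.78 against 2.34 at 20% (about 19% wider). Its test is essentially the ITT test, so it adds an estimate but no power. If assignment alone raises uptake in non-users by d points, the estimate is too high by f·d/(1 − f): for d = 2, 0.05 × 2/0.95 = 0.1 point at 5% non-use and 0.2 × 2/0.8 = 0.5 at 20%.

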### 2.1 VARIABLES

#### 2.1.1 Background and demographic characteristics

Demography and baseline characteristics will be statistically summarized by treatment group.

Demographic variables include age, gender, race and ethnicity, income, parental income, educational attainment, housing status and language spoken at home.

Baseline behavioral variables include variables related to potential HIV exposure, including: sexual and drug use behaviors, past diagnoses of sexually-transmitted-infections, as well as reproductive behaviors including: pregnancy status and desire, contraceptive use.

#### 2.1.2 Outcomes

##### 2.1.2.1 Primary outcome variables

- **PrEP prescriptions:** The number of participants who received a PrEP prescription and date of prescription, obtained by chart extraction from the medical record.

##### 2.1.2.2 Secondary variables

- **Number of Patients Reporting PrEP use:** Participants will be contacted at follow-up and asked if took PrEP in the past 3 months regardless of where it was obtained.

- **Patient-Perceived HIV risk:** Participants will be asked about how worried they are about getting HIV in the next 6 months.
- **Knowledge of PrEP:** Participants will be asked a series of questions about PrEP to assess PrEP knowledge.
- **Decisional Conflict:** Participants will be asked questions derived from the Decisional Conflict Scale to provide a measure of decision quality about their HIV prevention decision immediately following their visit.
- **Interpersonal Quality of HIV Prevention Care:** A scale for patient-centered HIV prevention counseling focusing on patient preferences and reflecting satisfaction and confidence in the counseling session, derived from the Interpersonal Quality of Family Planning Care Scale developed by the PI.
- **Intention to Use Any HIV Prevention Method:** Participants will be asked if they plan to use any HIV prevention method after the initial visit.
- **Satisfaction with Information Received about HIV Prevention:** Participants will be asked about their satisfaction with HIV prevention counseling.
- Confidence in decision to use an HIV prevention method. A one-time, one-item measure of certainty of plan to use HIV prevention after the initial visit. Participants can select from 4 options: 1 ("completely unsure"), 2 ("mostly unsure"), 3 ("mostly sure, but not 100%"), or 4 ("100% sure").
- **Perceived Quality of Information Received about HIV Prevention:** Participants will also be asked questions about the perceived quality of the HIV prevention information they received during their health care visit.
- **Acceptability of HIV Prevention Methods:** Participants will be asked to rate their preference for a method (even if they never used it). Participants can select from condoms, PrEP, PEP, treatment as prevention, regular partner testing, or other method.
- **Acceptability of the Decision Support Tool:** Participants in the experimental arm are asked four questions about their experiences using the DST.
- Perception of the Decision Support Tool: Participants in the experimental arm will be asked about the degree to which they liked/disliked the tool. Response options vary: "I did not like it at all", "I somewhat disliked it", "I somewhat liked it", "I really liked it".
- Willingness to Use the Decision Support Tool at Future Visits: Participants in the experimental arm will be asked about whether they would use the tool again if they returned to the clinic. Response options are "yes", "no", "unsure".
- Recommend the Decision Support Tool: Participants in the experimental arm will be asked whether they would recommend the tool a friend. Response options are "yes", "no", "unsure".
- Satisfaction with the Decision Support Tool: Participants in the experimental arm will be asked about the degree to which they were satisfied with the information in the tool. Response options vary from 1-5: "very unsatisfied" to "very satisfied".
- HIV Prevention Method Use (any method – planned or new method): A self-reported measure of HIV prevention method use, including those who reported discontinuing the initial HIV prevention method(s) that were reported post-clinic visit. A response of "yes" to any of the following questions: since your [baseline] visit, have you used....for HIV prevention – abstinence, condoms, PEP, PrEP, regular HIV testing, treatment as prevention, regular sexually transmitted disease (STD) testing, other method. The outcome will be dichotomized to those who responded affirmatively vs other responses ("no"/"unsure").
- **HIV Prevention Method Continuation:** A self-reported measure of HIV prevention method continuation.

- **HIV Prevention Method Use:** A self-reported measure of HIV prevention method use, including those who reported discontinuing the initial HIV prevention method(s) that were reported post-clinic visit.

### 2.1.3 Other metrics

- Percentage of missing answers in questionnaires
- Response times per questionnaire

## 2.2 Hypotheses

1. The intervention will result in significantly higher number of PrEP prescriptions compared to the control group.
2. The intervention will result in significantly higher number of individuals reporting PrEP initiation compared to the control group.
3. The intervention will result in significantly higher level of patient-perceived HIV risk post-visit compared to the control group.
4. The intervention group will report significantly higher PrEP knowledge compared to the control group.
5. The intervention group will report significantly higher quality of HIV care compared to the control group.
6. The intervention group will report significantly higher intention to initiate any HIV prevention method compared to the control group.
7. The intervention group will report significantly higher satisfaction with information received about HIV prevention compared to the control group.
8. The intervention group will report significantly higher confidence in decision to use an HIV prevention method compared to the control group.
9. The intervention group will report significantly higher acceptability of HIV prevention methods compared to the control group.
10. The intervention group will report significantly lower decisional conflict, as documented by the full scale and subscales, compared to the control group.
11. The intervention will result in significantly higher number of individuals reporting ongoing PrEP use at 3 months post-visit compared to the control group.
12. A significantly higher proportion of the intervention group will report use of any HIV prevention method at 3 months-post study initiation compared to the control group.
13. A significantly higher proportion of the intervention group will report significantly higher continuation of any HIV prevention method at 3 months-post study initiation compared to the control group.
14. The intervention group will report high acceptability of the DST.
15. A high proportion of the intervention group will report positive impression of the DST.
16. A high proportion of the intervention group will report willingness to use the DST at a future visit.
17. A high proportion of the intervention group will report willingness to recommend to a friend.
18. The intervention group will report high satisfaction with the DST.

## 1. STATISTICAL METHODOLOGY

### 3.1 General methodology

All outcomes will be presented using descriptive statistics; normally distributed data by the mean and standard deviation (SD) and skewed distributions by the median and interquartile range (IQR). Demography and baseline characteristics will be statistically summarized by treatment group. For binary or categorical items, counts and proportions will be calculated and reported. For continuous outcomes, we will use t-tests for independent samples and for categorical outcome we will employ  $\chi^2$  or Fisher's exact-tests to examine baseline differences between training and control group in demographic data or measured variables. Categorical variables will be assessed and collapsed in cases of small cell sizes for increased power. Scale items of questionnaires (e.g., Decisional Conflict Scale) will be recoded (where applicable) and a scale mean or sum score will be calculated and reported. Composite scale variables will be assessed for skewness through histograms and normal Q-Q plots. Where the normality assumption is not met, median and IQR will be reported. Sign tests will be used to detect differences between groups. Further, in instances where a strong skew is detected, scales will be transformed into binary variables and analyzed as binary data.

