7. DATA COLLECTION AND ANALYSIS

7.1 Outcomes of Interest

The primary outcome will be PrEP initiation within 3 months of the initial visit, as measured by PrEP prescriptions ascertained from chart review. Secondary outcomes include self-report of PrEP use at 3 months, as well as perceived HIV risk, knowledge of and interest in PrEP, decisional conflict, and interpersonal quality of HIV prevention care.

7.1.1 *Primary outcome*

- **PrEP prescriptions:** The number of participants who received a PrEP prescription and date of prescription, obtained by chart extraction from the medical record.

7.1.2 *Secondary outcomes*

- **Number of Patients Reporting PrEP use:** Participants will be contacted at follow-up and asked if took PrEP in the past 3 months regardless of where it was obtained.
- **Patient-Perceived HIV risk:** Participants will be asked about how worried they are about getting HIV in the next 6 months.
- **Knowledge of PrEP:** Participants will be asked a series of questions about PrEP to assess PrEP knowledge.
- **Decisional Conflict:** Participants will be asked questions derived from the Decisional Conflict Scale to provide a measure of decision quality about their HIV prevention decision immediately following their visit.
- **Interpersonal Quality of HIV Prevention Care:** A scale for patient-centered HIV prevention counseling focusing on patient preferences and reflecting satisfaction and confidence in the counseling session, derived from the Interpersonal Quality of Family Planning Care Scale developed by the PI.
- **Intention to Use Any HIV Prevention Method:** Participants will be asked if they plan to use any HIV prevention method after the initial visit.
- **Satisfaction with Information Received about HIV Prevention:** Participants will be asked about their satisfaction with HIV prevention counseling.
- **Perceived Quality of Information Received about HIV Prevention:** Participants will also be asked questions about the perceived quality of the HIV prevention information they received during their health care visit.
- **Acceptability of HIV Prevention Methods:** Participants will be asked to rate their preference for a method (even if they never used it). Participants can select from condoms, PrEP, PEP, treatment as prevention, regular partner testing, or other method.
- **Acceptability of the Decision Support Tool:** Participants in the experimental arm are asked four questions about their experiences using the DST.

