7.3 Quantitative Data Collection

Data from surveys will be entered into REDCap by participants with the use of a tablet computer, and by research staff in real-time over the phone during follow-up.

After obtaining informed consent, research staff will explain and administer the pre-visit survey, which collects information on HIV prevention knowledge and interest, before the intervention participants use the decision support tool.

After the participant's visit with the provider, they will be asked to complete a post-visit survey about their clinic visit and counseling, risk perception, decision making, sexual history, and their experience with the decision support tool if they are in the intervention arm.

Three months post-visit, research staff will follow-up with participants by phone to administer a short survey and ask participants about their chosen HIV prevention method, and if they initiated PrEP.

Upon completion of the study, research staff will extract data from the medical record pertaining to participants' PrEP prescriptions, history of sexually transmitted infections, zip code, and insurance status.

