### 1.2 Study Design and Randomization

The study is a parallel-group Randomized Control Trial with up to 384 participants recruited from family planning sites in Duval County, Florida and randomized 1:1 into two groups (192 in intervention group, 192 in control). Study duration: 3 months.

Treatment: Participants in this arm will receive the HIV prevention DST intervention and will receive the intervention immediately before their provider visit.

Control: Participants in this arm will receive usual care.

Randomization procedures: Randomization will be implemented using randomly permuted blocks of randomly selected size 2 and 4, stratified by clinic and race. All randomization will occur by research staff with the use of a REDCap randomization instrument.

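### Baseline data enter no outcome analysis: H1 ignores the pre-visit interest item, and the stated outcome of interest in PrEP has no definition, hypothesis or test

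*SAP*

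**What the plan says.** **Baseline data.** SAP 2.1.1 and 3.1 summarise demographic and baseline variables by arm. SAP 3.1 adds t-tests and chi-square or Fisher's exact tests "to examine baseline differences between training and control group in demographic data or measured variables". SAP 4.2 imputes missing baseline characteristics by chained equations. SAP 1.2 stratifies the randomisation by clinic and race.

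**Pre-visit survey.** Protocol 7.3 describes a survey "which collects information on HIV prevention knowledge and interest, before the intervention participants use the decision support tool". Protocol 3.2.3 describes the same survey as covering experience and knowledge, and does not mention interest.

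**Primary analysis.** SAP 3.3.1 says "Differences in PrEP prescriptions between groups will be examined by" a chi-square or Fisher's exact test. No covariate or stratum is named.

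**Outcomes.** The summary paragraph of Protocol 7.1 lists self-reported PrEP use as a secondary outcome, "as well as perceived HIV risk, knowledge of and interest in PrEP, decisional conflict" and interpersonal quality of care.

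**Design figures.** SAP 1.5 states that "a sample of 320 women will provide 80% power in two-sided tests with alpha of 0.05" for a rise in PrEP uptake "from 5% among controls to 15% in the intervention arm". SAP 1.2 allocates 192 women to each arm.

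**The concern.** There are three parts, of unequal weight.

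1. A pre-visit answer about interest is a plausible predictor of who leaves with a PrEP prescription, and the protocol says it is collected. Leaving it out of H1 gives up precision that costs almost nothing to recover.
2. Interest in PrEP is a stated secondary outcome on the tool's intended pathway (Protocol 1.1 says the tool should help women identify their own interest in PrEP). An outcome with no definition or test cannot be reported as pre-specified. A measurement taken only before the tool is used cannot show an effect of the tool.
3. If randomisation is carried out properly, any baseline difference between arms is due to chance, so a p-value for it answers no question. With no covariates fixed in advance, a small p-value may prompt adjustment after the fact.

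**Working it through.** **Step 1: reproduce the plan's sample size.** The inputs are 5% and 15%, two-sided alpha 0.05 and 80% power (SAP 1.5). The mean rate is 0.10.

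Uncorrected n per arm = [1.960 × √(2 × 0.10 × 0.90) + 0.842 × √(0.05 × 0.95 + 0.15 × 0.85)]² / 0.10² = 140.1, so 141 per arm and 282 in total.

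With continuity correction, n = (140.1/4) × [1 + √(1 + 4/(140.1 × 0.10))]² = 159.5, so 160 per arm and 320 in total. This matches the stated figure. The plan's calculation is therefore reproduced by an unadjusted two-proportion comparison with no baseline term.

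**Step 2: power of H1 as planned, at 5% versus 15%.**

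| Per arm | Normal approximation | Fisher's exact |
|---|---|---|
| 154 (384 × 0.80 / 2, rounded) | 83.6% | 81.0% |
| 160 | 85.0% | 82.4% |
| 192 | 90.7% | 89.1% |

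The unadjusted test meets 80% in every row.

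**Step 3: what adjustment would add.** The documents give neither the share of women interested before the visit nor how strongly interest predicts prescription. Both are assumptions here. Interest is taken as binary, and the rates within each arm are set so that the arm totals stay at 5% and 15%. The comparison is an uncorrected chi-square test against a Mantel-Haenszel test stratified on interest. The Mantel-Haenszel statistic is Σ(x − M·t/N) / √Σ[M(N − M)·t·c / (N²(N − 1))], where in each stratum x is the prescriptions in the tool arm, M all prescriptions, t and c the arm sizes, and N = t + c. Simulated power with 192 per arm (40,000 trials per setting):

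| Odds ratio, interest with prescription | 30% interested: unadjusted → adjusted | 50% interested: unadjusted → adjusted |
|---|---|---|
| 1 | 91.9% → 91.8% | 92.2% → 92.0% |
| 3 | 92.0% → 92.5% | 92.0% → 92.4% |
| 6 | 92.0% → 93.6% | 92.1% → 93.1% |
| 12 | 92.1% → 94.7% | 92.3% → 93.7% |

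With the association expressed instead as a risk ratio equal in both arms and 27% interested, power rises from about 92% to 92.3% at a ratio of 2, 92.6% at 3, 93.8% at 5 and 95.3% at 10. The last case is demanding. The rate among uninterested women in the tool arm would be 0.15 / (0.73 + 0.27 × 10) = 4.4%, so about 44% of interested women would have to be prescribed PrEP.

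If interest predicts tenfold in controls but only one- to twofold in the tool arm, the gain is 0.3 to 0.9 points. Across all settings the gain is about 0 to 4 points. With no association the loss is under 0.5 points.

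**Step 4: follow interest in PrEP through the documents, with knowledge of PrEP alongside.**

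| Place | Knowledge of PrEP | Interest in PrEP |
|---|---|---|
| Protocol 7.1, summary paragraph | named | named |
| Protocol 7.1.2, itemised outcomes | defined | absent |
| SAP 2.1.2.2, secondary variables | defined | absent |
| SAP 2.2, hypotheses 1 to 18 | H4 | absent |
| SAP 3.3, analyses | tested with H2 to H9 | absent |

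H6 does not replace it, because it counts intention to use any method: choosing condoms scores the same as choosing PrEP. H9 compares ratings across methods, and no PrEP-specific comparison is defined.

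**Step 5: baseline tests.** The chance of at least one p < 0.05 among k independent tests under correct randomisation is 1 − 0.95^k: 40% for k = 10, 54% for k = 15 and 64% for k = 20. Both k and independence are assumptions.

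**The case against.** The strongest reply is that nothing here makes H1 wrong. The unadjusted test is valid under randomisation and has more than its stated power on the plan's own inputs. That stands, and it rules out reading the point as bias or as a shortfall in power.

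Four other inferences are tempting, and the documents do not support them.

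- *Baseline data are used only for significance tests.* They are also summarised by arm and imputed, and race and clinic are used to stratify the randomisation. What is true is that no baseline value enters an outcome comparison.
- *The pre-visit survey measures interest in PrEP.* Protocol 7.3 refers to HIV prevention in general, Protocol 3.2.3 omits interest, and the survey items are not shown. Protocol 1.1 says women know little about prevention options, so a pre-tool answer may predict poorly.
- *PrEP interest after the visit cannot be reported.* The post-visit survey asks about method choice (Protocol 3.2.3), and the acceptability item, compared under H9, lists PrEP among the methods. These cover part of the ground, and a suitable post-visit item may exist. The supportable statement is that no analysis of interest in PrEP is planned.
- *The baseline tests will distort the primary result.* SAP 3.3.1 fixes the H1 test and attaches no decision to a baseline p-value. Deleting the tests changes no result.

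**Conclusion.** The point holds as an efficiency gain for H1 and a mismatch between the protocol and the SAP over one secondary outcome. Adjusting H1 for pre-visit interest is worth about 0 to 4 points of power at 5% versus 15% with 192 per arm. The upper end needs a strong association that is similar in both arms, and the whole range rests on assumed values and on the interest item having been collected. The absence of interest in PrEP from every definition, hypothesis and analysis is a matter of text and needs no assumption. The baseline significance tests are uninformative, but removing them is housekeeping.

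**What to change.** 1. **H1.** Confirm from the survey form that an interest item was collected. If so, pre-specify in SAP 3.3.1, before outcomes are seen by arm, an analysis stratified by or adjusted for that item as collected (for example Mantel-Haenszel), and report the adjusted risk difference with its 95% confidence interval. Cost: SAP wording, and a power loss under 0.5 points if interest does not predict prescription.
2. **Interest in PrEP.** Reconcile Protocol 7.1 with Protocol 7.1.2 and the SAP. If the post-visit survey has no such item and recruitment is open, add one, define the outcome, and compare arms adjusted for the pre-visit value. Otherwise remove it as an outcome. Cost: one survey item, which will be missing for women already surveyed.
3. **Baseline table.** Delete the significance tests from SAP 3.1 and keep the summary by arm. This loses nothing that the plan uses.
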